# 9.3 Demographics and Baseline Characteristics

Patient disposition, demographics and baseline characteristics, AML status (PIF/ER) and prior therapy, AML subclassifications and cytogenetics, and medical history will be summarized.

# 9.4 Study Drug Exposures and Concomitant Medications

Study drug exposures and concomitant medications will be summarized by descriptive statistics. Dose intensity will be calculated as the percentage of dose actually administrated divided by the intended dose during the treatment period and up to the last dose on study drug. Dose intensity will be summarized by cycle.

# 9.5 Safety Endpoint(s) and Analyses

## 9.5.1 Adverse Events

Adverse events will be coded to the Medical Dictionary for Regulatory Activities (MedDRA). Only TEAEs, as defined in Section 7.11.1 will be summarized in tables. Events prior to treatment (e.g., due to study-related procedure) will be listed in an appendix to the final study report. DLTs will be listed.

The following tables of AE data will be created to summarize the number and percent of patients who experience at least one event of each of the following types:

- All AEs
- Drug-related AEs
- AEs by CTCAE Grade
- Drug related AEs by CTCAE Grade
- AEs with CTCAE Grade severity  $\geq$  Grade 3
- Drug-related AEs with CTCAE Grade severity  $\geq$  Grade 3
- SAEs (this may be a listing if there are few events)
- Drug-related SAEs
- Fatal AEs (this may be a listing if there are few events)
- AEs that result in study discontinuation
- AEs that lead to withdrawal of study drug
- AEs categorized as AESI and/or IREs

Tabulated data will display the number and percent of patients that experience individual events by System Organ Class (SOC) and Preferred Term (PT). Events will be displayed alphabetically for SOC and in descending order of overall PT incidence within each SOC.

An overall summary of AEs will display the number and percent of patients who experience at least one event of each of the following types:

- Any AE
- Any drug-related AE

- Any AE with CTCAE Grade severity  $\geq$  Grade 3
- Any drug-related AE with CTCAE Grade severity  $\geq$  Grade 3
- Any SAE
- Any drug-related SAE
- Any AE that results in study or study drug discontinuation
- Any fatal AE
- Any AESI
- Any IREs

## 9.5.2 Laboratory Values

Summaries of laboratory values will display descriptive statistics for numerically quantified labs. Summaries will be grouped by lab panel (e.g., hematology, blood chemistry, and urinalysis) and will be displayed by visit for each lab parameter. Graphs of mean values over time or individual values at each time point may be used.

Shift tables will be used to display the percent of patients who have a shift in their lab values from normal at baseline to each post-baseline visit by CTCAE v4.0 severity Grade.

## 9.5.3 Other Safety Endpoints

Electrocardiograms will be collected and analyzed for evidence of cardiac toxicity, especially prolongation of QT interval. Vital signs will be summarized with descriptive statistics at each visit and time point where they are collected.

# 9.6 Efficacy Endpoints and Analyses

Disease activity will be assessed by the study investigators, by using CBC and peripheral blood cell morphological examination, examination of bone marrow aspiration (or biopsy if required), and physical examination. Modifications to the Revised Recommendations of the International Working Group for Diagnosis (IWG), Standardization of Response Criteria, Treatment Outcomes, and Reporting Standards for Therapeutic Trials in Acute Myeloid Leukemia will be used (Appendix 3). Response assessment will be based on bone marrow aspirate/biopsy and the best CBC up to 14 days post bone marrow aspirate/biopsy. Responses will be categorized as:

- CR (mCR [morphologic CR], CRc [cytogenic CR], or CRm [molecular CR]);
- CRh;
- CRi (CRn [CR with incomplete neutrophil recovery]; CRp [CR with incomplete platelet recovery]);
- MLFS;

- PR;
- OB;
- SD;
- PD.

The number and percent of PIF/ER AML patients will be summarized by best overall response. Efficacy analyses will be based on the PIF/ER AML population (see **Inclusion Criterion 2**). All efficacy results will be summarized by PIF, ER and the total combined PIF/ER populations.

# 9.6.1 Primary Efficacy Analysis

The primary efficacy endpoint for the AML expansion cohort is the CR/CRh rate, calculated as the proportion of patients in the efficacy population that has achieved a best response of CR (mCR, CRc, or CRm) or CRh at any point during treatment by investigator's assessment, according to IWG AML response criteria (Appendix 3). CR/CRh rate will be summarized for the total combined PIF/ER patients as the primary analysis, as well as for PIF and ER patients separately, and for PIF/ER patients in the response-evaluable population as a sensitivity analyses. A two-sided exact 95% confidence interval will be calculated around response rates.

For the second interim analysis of 100 patients, as well as for the final analysis of 170 patients, all treated patients will be followed for at least 6 months or until death from any cause, whichever occurs first, prior to data cutoff for the analysis. If the trial passes the prespecified efficacy boundary (25% observed CR/CRh rate) at the second interim analysis, a two-sided exact 95% confidence interval as described by Jennison and Turnbull (21) will be produced to account for the bias in the conventional exact confidence interval for fixed sample test.

# 9.6.2 Secondary Efficacy Analyses

Counts, percentages, and two-sided exact 95% confidence intervals will be used to describe categorical secondary variables. Kaplan-Meier (KM) methods will be used to estimate time-to-event endpoints, unless otherwise specified. All secondary efficacy endpoints will be summarized in both efficacy and response evaluable population by PIF, ER, and total.

# 9.6.2.1 Key Secondary Efficacy Analyses

The key secondary efficacy endpoints include CR rate, CRh rate, duration of response, postbaseline transfusion independence rate, HSCT rate, and incidence and duration of hospitalization.

**Duration of response (DOR)** will be calculated from the time of initial documentation of response to the time of disease relapse or death due to any cause, whichever occurs first. Patients who are still in response at study completion without alternative therapies will be censored at the time of their last disease assessment. Duration of response will be calculated

for patients who achieve the first evidence of CR or CRh as primary analysis. A separate exploratory analysis will be conducted for patients who achieve the first evidence of overall complete response (CR, CRh, CRi [CRn, CRp], or MLFS).

**Post-baseline transfusion independence** is defined as no transfusion during any consecutive 56-day period on-study. Post-baseline transfusion independence will be summarized for RBC and platelet transfusion separately and in total. Transfusion dependence at baseline is defined as any red blood cell or platelet transfusions during the 28 days prior to the first dose of study drug. The rate of conversion from transfusion dependence to transfusion independence will be calculated. The rate of patients who are transfusion independent at baseline and remain independent during any 56-day post-baseline period will also be calculated.

**HSCT rate** is defined as rate of successful HSCT through study treatment. Patients who received other therapies (except for conditioning therapy) for AML after discontinuation of study drug and later undergo a subsequent HSCT will not be included. Number and percentage of patients with HSCT will be summarized.

**Incidence and Duration of Hospitalization,** summaries will be provided for the efficacy population, as well as independently for patients who achieved CR or CRh. Summaries will include duration of initial hospitalization as well as incidence, number and duration of subsequent hospitalizations following the initial discharge, number of days hospitalized, and the reasons for hospitalization.

# 9.6.2.2 Additional Secondary Efficacy Analyses

Additional secondary efficacy endpoints include overall complete response rate, objective response rate, subgroup analyses of CR/CRh, CR, CRh and overall complete response rates, overall survival, event-free survival, time to response, mortality rate at 30, 60, 90, and 180 days, six-month and one-year survival.

**Overall complete response rate (OCRR)** is defined as the rate of CR+CRh+CRi [CRn, CRp]+MLFS according to IWG AML response criteria (**Appendix 3**), and includes any response which achieves < 5% BM blasts by morphology.

**Objective response rate** is defined as the rate of CR+CRh+CRi [CRn, CRp]+MLFS+PR according to IWG AML response criteria (**Appendix 3**).

Subgroup analyses of CR/CRh, CR, CRh, and overall complete response rates will be performed by baseline disease characteristic (e.g., age group [ $< 70, \ge 70$ ], gender, cytogenetic risk status [high, intermediate, low], prior line of therapy [1, 2, 3], TP53 gene mutations).

**Overall survival** is defined as the time between the date of the first dose of study drug and death from any cause. Patients who are alive or whose death status is unknown will be censored at the last date known to be alive on or before the data cutoff date.

**Event-free survival** is defined as the time from the first dose of study drug until date of relapse from CR, CRh, or CRi (CRn, CRp), or death from any cause, whichever occurs first.

Patients who are not known to have any of these events at study completion will be censored at the date of the last disease assessment.

**Time to response** (TTR) is defined as time from first dose of study drug to first CR, CRh, CRi (CRn, CRp), or MLFS, and will be summarized with descriptive statistics. Time to CR/CRh and time to best overall response will be calculated.

**Mortality rate** is defined as rate of death from any cause within 30, 60, 90, or 180 days of first dose of study drug.

**Six-month survival rate** is defined as the probability of survival at 6 months from first dose of study drug.

**One-year survival rate** is defined as the probability of survival at 1 year from first dose of study drug.

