The overall complete response rate (BM blasts < 5%) will be the proportion of patients with AML achieving any CR, CRh, CRi, [CRn, CRp], or MLFS when such responses are documented at any point of any cycle of treatment. The objective response rate will be the proportion of patients with AML achieving CR, CRh, CRi, [CRn, CRp], MLFS, or PR when such responses are documented at any point of any cycle of treatment. To support the composite endpoint CR/CRh, the duration of initial hospitalization for flotetuzumab administration, the incidence and duration of subsequent hospitalizations, and transfusion independence rate, as well as rate of conversion to transfusion independence and rate of maintenance of transfusion independence, will be assessed. The timing of the AML response evaluation, i.e., the allowance for response at a time later than Day 25 from the start of treatment, differs from those modified from the IWG guidelines for AML (which are based on responses to cytotoxic chemotherapy) to allow sufficient time for an immune-mediated response to be observed. Patients who do not demonstrate an objective response at early evaluations, may be subsequently categorized as responders at later evaluations. Response duration will be calculated from the time of initial response to the time of relapse or death, whichever occurs first. Patients who complete the study while still in response will be

censored at their last disease assessment. Time to response will be calculated from the time of first dose of study drug to the time of initial response.

Event-free survival (EFS) will be calculated as the time from the first dose of study drug until date of relapse from CR, CRh, or CRi (CRn, CRp), or death from any cause, whichever occurs first.

Overall survival (OS) will be calculated as the time from the first dose of study drug until the occurrence of death from any cause. Mortality rates from any cause within 30, 60, 90, and 180 days from the first dose of study drug will be calculated. Six-month and one-year survival rates will be calculated.

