Progressive disease	NA	NA	NA	
 
Evidence for an increase in bone marrow blast percentage and/or increase of absolute blast counts in the blood:
 
> 50% increase in marrow blasts over baseline (a minimum 15% point increase is required in cases with < 30% blasts at baseline; or persistent marrow blast percentage of > 70% over at least 3 mo; without at least a 100% improvement in ANC to an absolute level (>0.5 x 10^9/L [500/mL], and/or platelet count to >50 x 10^9/L [50 000/mL] non-transfused); or
 
> 50% increase in peripheral blasts (WBC x % blasts) to > 25 x 10^9/L (> 25 000/mL) (in the absence of differentiation syndrome)†; or
 
New extramedullary disease
 
	In general, at least 2 cycles of flotetuzumab should be administered to determine "progressive disease". "Progressive disease" is usually accompanied by a decline in ANC and platelets, increased transfusion requirement, and decline in performance status or increase in symptoms		
Recurrence/relapse	Relapse after CR is defined as a reappearance of leukemic blasts in the peripheral blood and $\geq$ 5% blasts in the bone marrow not attributable to any other cause (e.g., bone marrow regeneration after consolidation therapy)						

CR = complete remission (includes mCR, CRc, CRm).

 $CRi = includes neutrophil count \ge 1000 \text{ or platelet count} \ge 100,000.$ 

\*Assessment is quantitated by BM biopsy and best CBC (up to 14 days post BM biopsy).

# No RBC and/or platelet transfusion within 5 days prior to response assessment.

§ No platelet transfusion within 5 days prior to response assessment

† Certain targeted therapies, for example, those inhibiting mutant IDH proteins, may cause a differentiation syndrome, that is, a transient increase in the percentage of bone marrow blasts and an absolute increase in blood blasts; in the setting of therapy with such compounds, an increase in blasts may not necessarily indicate PD.

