6.2 Secondary Efficacy Endpoints

Key secondary endpoints are listed in Table 3.

Table 3Key Secondary Endpoints

Name	Description
Duration of response (DOR)	Time of initial documentation of response to the time of disease relapse or death due to any cause, whichever occurs first.
Rate of post-baseline transfusion independence	Rate of no transfusion during any consecutive 56-day period on-study.
Rate of HSCT	Rate of successful HSCT through study treatment.
Incidence and duration of hospitalization	Duration of initial hospitalization as well as incidence, number and durations of subsequent hospitalizations following the initial discharge, number of days hospitalized, and reasons for hospitalization.
CR rate	Rate of complete remission.
CRh rate	Rate of complete remission with partial hematologic recovery.

The additional secondary endpoints are listed in Table 4.

Name	Description
Overall complete response rate	Rate of achievement of BM blast of < 5%, CR+CRh+CRi [CRn, CRp]+MLFS according to IWG AML response criteria.
Objective response rate	Rate of CR+CRh+CRi [CRn, CRp]+MLFS+PR according to IWG AML response criteria.
Overall survival (OS)	Time from first dose to death from any cause.
Event-free survival (EFS)	Time from first dose to the date of relapse after CR/CRh/CRi [CRn, CRp], or death from any cause, whichever occurs first.
Time to response (TTR)	Time from first dose to the first CR, CRh, CRi (CRn, CRp), or MLFS.
Mortality rate at 30, 60, 90 and 180 days	Rate of death from any cause within 30, 60, 90, 180 days of first study dose.
Six-month survival rate	Probability of survival at 6 months from first study dose.
One-year survival rate	Probability of survival at 1 year from first study dose.
Immunogenicity	Proportion of patients who become positive for anti-drug antibody production.
Pharmacokinetics	Evaluation of serum concentration of flotetuzumab and its relationships with efficacy, safety and correlative endpoints.

Table 4 Additional Secondary Endpoin	ble 4	Additional Secondary Endpoints
--------------------------------------	-------	--------------------------------

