11.2.2 Additional Secondary Efficacy Analyses

Additional secondary efficacy endpoints include overall complete response rate, objective response rate, subgroup analyses of CR/CRh, CR, CRh and overall complete response rates, overall survival, event-free survival, time to response, mortality rate at 30, 60, 90, and 180 days, six-month and one-year survival.

Overall complete response rate is defined as the rate of CR+CRh+CRi [CRn, CRp]+MLFS according to IWG AML response criteria (**Appendix 1**), and includes any response which achieves < 5% BM blasts by morphology.

Objective response rate is defined as the rate of CR+CRh+CRi [CRn, CRp]+MLFS+PR according to IWG AML response criteria (**Appendix 1**).

Subgroup analyses of CR/CRh, CR, CRh, and overall complete response rates will be performed by baseline disease characteristic (e.g., age group [$< 70, \ge 70$], gender, cytogenetic risk status [high, intermediate, low], prior line of therapy [1, 2, 3], TP53 gene mutations)

Overall survival (OS) is defined as the time between the date of the first dose of study drug and death from any cause. Patients who are alive or whose death status is unknown will be censored at the last date known alive on or before data cutoff date. The last known-to-be-alive date is the last non-imputed date of any subject record in the study database. This date may be the last visit date or last contact date that the subject is known to be alive.

OS (months) = (date of death or last known alive – first dose date +1) / (365.25/12)

Event-free survival (EFS) is defined as the time from the first dose of study drug until date of evidence of relapse from CR, CRh, or CRi (CRn, CRp), or death from any cause, whichever occurs first. Patients who are not known to have any of these events at study completion will be censored at the date of the last disease assessment.

EFS (months) = (date of event [relapse or death] or date of censoring – first dose date + 1) / (365.25/12)

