Sensitivity analysis of OS and EFS: patients will be censored for alternative therapies or procedures such as surgery, HSCT, radiation and subsequent antileukemic therapy, etc. If a patient begins a subsequent antileukemic therapy prior to event, the patient will be censored at the date of last assessment before starting the new anti-cancer therapy. For EFS, patients with two or more consecutive missing response assessments prior to event will be censored at the last date of response assessment before the missing assessments.

Time to response (TTR) is defined as time from first dose of study drug to first CR, CRh, CRi (CRn, CRp), or MLFS and will be summarized with descriptive statistics. Time to CR/CRh and time to best overall response will be calculated.

Mortality rate is defined as rate of death from any cause within 30, 60, 90, or 180 days of first dose of study drug. Number and percentage of deaths at 30, 60, 90, or 180 days will be summarized.

Six-month survival rate is defined as the probability of survival at 6 months from first dose of study drug.

One-year survival rate is defined as the probability of survival at 1 year from first dose of study drug.

Six-month and one-year survival rates will be evaluated by KM estimate with 95% CI.

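### EFS counts only relapse from CR/CRh/CRi or death, so for patients who never reach those responses it adds no event beyond OS; a companion EFS that counts treatment failure would be a cheap improvement

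*Protocol*

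**What the plan says.** EFS is defined in four places, always with the same two events.

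- Protocol 7.10: "Event-free survival (EFS) will be calculated as the time from the first dose of study drug until date of relapse" from CR, CRh or CRi, or death.
- Protocol 9.6.2.2: "until date of relapse from CR, CRh, or CRi (CRn, CRp), or death from any cause, whichever occurs first".
- SAP 6.2, Table 4: "Time from first dose to the date of relapse after CR/CRh/CRi [CRn, CRp], or death from any cause, whichever occurs first".
- SAP 11.2.2 repeats this and adds the censoring rule: "Patients who are not known to have any of these events at study completion will be censored at the date of the last disease assessment".

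The EFS sensitivity analyses in SAP 11.2.2 add censoring and no events. For example: "If a patient begins a subsequent antileukemic therapy prior to event, the patient will be censored at the date of last assessment" before that therapy.

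MLFS is treated as a response elsewhere. Time to response "is defined as time from first dose of study drug to first CR, CRh, CRi (CRn, CRp), or MLFS". MLFS also counts in the overall complete response rate (OCRR) and in the exploratory DOR analysis (Protocol 9.6.2.1 and 9.6.2.2; SAP 11.2.1 and 11.2.2).

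On relapse, Protocol Appendix 3 says: "Relapse after CR is defined as a reappearance of leukemic blasts in the peripheral blood" together with at least 5% marrow blasts. A footnote there reads "CR = complete remission (includes mCR, CRc, CRm". SAP Appendix 1 has the same text.

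**The concern.** EFS is a named secondary objective (Protocol 3.2). Its usual purpose is to show how long patients stay free of both death and failure of treatment. Here, a patient with refractory disease, with progression after PR, or who loses MLFS stays event-free until death. The plan recognises such outcomes elsewhere: Protocol 4.1 speaks of determining treatment failure, Protocol 5.4 lists insufficient response and progression as grounds for withdrawal, and Protocol 8.3.2 collects the date of disease progression. EFS uses none of them.

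At the response rates the trial is designed around, this group is likely to be the majority of the efficacy population. The EFS curve would then be driven mainly by deaths, and someone who looks at it without the definition could read it as a measure of disease control.

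**Working it through.** **The plan's own figures.** No event count or power is stated for EFS, so the only figures to reproduce are those of the CR/CRh design (Protocol 9.1, SAP 4.2). They serve here only to anchor the response rates. Exact binomial calculation over stages of 40, 60 and 70 patients, with boundaries 5/40, 15/100, 25/100 and 35/170, gives:

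- at 14.7%: overall one-sided alpha 0.0239 (stated 0.024), 0.0047 at the second interim (stated 0.005), early futility stop 0.546 (stated 55%);
- at 23%: power 0.787 with futility binding and 0.801 without (stated approximately 80%).

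All agree with the documents.

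**Events side by side.**

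| Course | OS event | EFS event as written |
|---|---|---|
| CR, CRh or CRi, then relapse | death | relapse |
| MLFS, then lost | death | death |
| PR, then progression | death | death |
| Progression or no response | death | death |

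In the last three rows the two event dates are identical. This follows from the definitions and needs no assumption.

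**How many patients.** The number whose only possible EFS event is death is 170 × (1 − r − c), where r is the CR/CRh rate and c the rate of patients whose best response is CRi. The documents give r but not c, so c = 0 gives an upper bound and the other columns are assumptions.

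| r | c = 0 | c = 10% | c = 25% |
|---|---|---|---|
| 23% (target) | 130.9 | 113.9 | 88.4 |
| 35/170 (success boundary) | 135.0 | 118.0 | 92.5 |
| 14.7% (null) | 145.0 | 128.0 | 102.5 |

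**Illustration only.** Suppose 30% reach CR/CRh/CRi (60% of them at the end of Cycle 1, 40% at the end of Cycle 2), median remission is 6 months and median survival of the others is 4 months, all exponential. None of these inputs is in the documents.

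- Responders still event-free at 6 months: 0.174 of all patients.
- Others alive at 6 months: 0.70 × 2^(−6/4) = 0.247.
- EFS as written: 0.174 + 0.247 ≈ 0.42.
- If a share f of the others never has a counted failure, and all counted failures fall before 6 months, failure-counting EFS is 0.174 + f × 0.247. This is 0.17, 0.22 and 0.25 for f = 0, 0.2 and 0.3.

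The difference is (1 − f) × (1 − R) × 2^(−6/m), with R the response share and m the median survival of the others. For R from 20% to 48% and m from 3 to 6 months it runs from 0.52 × 0.25 = 13 points to 0.80 × 0.50 = 40 points at f = 0, and from 9 to 28 points at f = 0.3. The f = 0 values are maxima: a patient in continuing PR has no event under either definition, and progression after PR can come later than 6 months.

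**The case against.** The strongest reply is that this is a deliberate endpoint choice. The definition is stated in advance and is the same in all four places. No section promises that EFS measures time to treatment failure, and EFS is an additional descriptive endpoint with no alpha and no planned comparison. That stands, and it rules out calling the definition an error.

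Much of the missing information is also reported elsewhere. Best overall response is tabulated by category, including stable and progressive disease (Protocol 9.6, SAP 11), and the exploratory DOR follows MLFS responders to relapse or death. That stands too, but it does not make the EFS curve informative about failure.

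The plan also has reasons for caution about early failure events. Protocol 4.1 reports that 3 of 21 patients with CR had an initial blast increase after Cycle 1. Protocol 7.10 lets later evaluations reclassify non-responders, and Appendix 3 generally asks for two cycles before progression is called. The criteria in 4.1 and 5.4 are treatment-stopping rules with different wording. An added definition must therefore set its own conventions.

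Four stronger readings are tempting and are not supported:

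- A reader might infer that EFS is biased by 13 to 40 points. Those figures compare two different endpoints on assumed inputs; they do not measure bias in the written one.
- A reader might infer that EFS duplicates OS for the whole trial. It does not: relapse is an event for CR/CRh/CRi responders.
- A reader might infer that censoring at the last disease assessment distorts the curve. Protocol 8.3.2 collects hematology and disease status every 3 months off treatment. If those count, which is the natural reading, the effect in simulation on assumed inputs is at most 0.5 points at 6 months and 1.9 at 12.
- A reader might infer that relapse from CRh or CRi cannot be judged. The Appendix 3 criterion rests on blasts alone, and CRh and CRi share the same marrow-blast threshold as CR, so it carries over; only the wording is missing.

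**Conclusion.** The point holds as a low-cost improvement. As written, EFS adds no event beyond OS for patients who never reach CR, CRh or CRi. That is at most 131 of 170 at the 23% target and 145 at 14.7%, fewer once CRi responders are removed. The bounds rest on the plan's response rates and full enrolment of 170; the CRi rate is unknown. Loss of MLFS is also not an EFS event, although MLFS counts as a response in OCRR, time to response and exploratory DOR.

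No stated figure is wrong. The EFS event list does not touch the primary test, sample size, DOR or OS. Any percentage-point gap between the two definitions is an illustration on assumed inputs and should be presented only as that.

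**What to change.** Keep the current definition, and state beside it that for patients never in CR, CRh or CRi it equals time to death. Then add to Protocol 9.6.2.2, and to the EFS sensitivity paragraph of SAP 11.2.2, a reported EFS whose event is the earliest of:

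- **(a)** documented treatment failure: Appendix 3 progression not overturned by a later documented response, progression after PR, or no PR or better after 2 cycles, dated at the assessment that established it;
- **(b)** relapse from CR, CRh or CRi, or loss of MLFS;
- **(c)** death from any cause.

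For (b), add a line to Protocol Appendix 3 and SAP Appendix 1 that applies the existing blast-based relapse criterion to CRh, CRi and MLFS, and use the same line for DOR.

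Three conventions are needed, for this analysis only:

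- Which PR definition applies. Protocol 4.1 and 5.4 use blasts alone, while Appendix 3 also requires neutrophil and platelet levels.
- How the two-cycle wording is reconciled for dating. Protocol 4.1 refers to at least two successive cycles, Protocol 5.4 simply to two cycles.
- What date is used when the Cycle 2 marrow is skipped, as Protocol 7.10 allows.

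No treatment rule changes. The cost is wording in four places (Protocol 9.6.2.2 and Appendix 3; SAP 11.2.2 and Appendix 1) and some programming. Response, progression and death dates are already collected. The added EFS curve will look less favourable than the current one.
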